10.6 Adverse drug reactions and reference safety information

10.6.1 Adverse drug reaction

An adverse drug reaction (ADR) is an undesirable and unintended response to a drug related to any administered dose. This definition implies a reasonable possibility of a causal relationship between the event and the investigational drug. This means that there are facts (evidence) or arguments suggesting a causal relationship.

Given that the investigational drugs have been commercially approved by ANVISA for decades, in this study only adverse reactions not yet described in ANVISA's drug dossier and assessed by the investigator as having a reasonable causal relationship with a drug (under investigation) will be considered ADRs. Thus, no reports of ADRs related to the drugs used in this study are expected.

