10.6.2 Safety Reference Information

Basic safety information (RSI) forms the basis for assessing the predictability of an AEF for accelerated reports and annual safety reports, as well as for the safety monitoring of clinical trial participants by regulatory agencies (or ethics committees). In the context of this study, no ADR reports are expected, as potential adverse reactions are expected to already be described in the SIR for the investigational drugs (, and ANVISA Drug Dossier, and the package insert for the drug registered with ANVISA), except in exceptional cases, for the investigational medical products in this study.

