10.7 Serious adverse event

10.7.1 Definition of a serious adverse event ()

A SAE is defined as any adverse medical event that, at any dose:

Results in death

Be life-threatening (the term “life-threatening” in the definition of severity refers to an event during which the participant was at risk of death; it does not refer to an event that hypothetically could have caused death if it had been more severe)

Require hospital admission or prolongation of an existing hospitalization. Hospitalizations for elective surgery (i.e., a planned, non-emergency medical procedure), social hospitalizations, and hospitalizations lasting less than 24 hours are not considered SAEs

Result in persistent or significant disability/impairment

Be a congenital anomaly/birth defect

Be a significant medical event (i.e., clinically significant)

Medical and scientific judgment must be exercised to decide whether prompt reporting is appropriate in other situations, such as for medically significant events that may not be an immediate life-threatening event or result in death or hospitalization, but that may put the participant at risk or require intervention to prevent one of the other outcomes listed in the definition above. These events should also be considered serious.

Any worsening of a pre-existing condition or any new condition that meets the above SAE criteria should be considered an SAE, and the investigator is encouraged to discuss with the study coordination any SAE for which the severity assessment is uncertain or questionable.

The following situations are not considered SAEs:

Elective or pre-planned surgery for a pre-existing condition that has not worsened

Routine health evaluations requiring hospitalization not associated with a deteriorating clinical condition

Social hospitalization (homelessness, family circumstances, etc.)

Adverse reactions associated with the investigational drugs, which are expected for such drugs according to the drug dossier registered with ANVISA

Results under investigation

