10.7.2 Reporting of serious adverse events

The SAE reporting period begins when the consent form is signed by the participant. The SAE reporting period ends at the 90-day visit.

The occurrence of an SAE must be reported immediately to the study monitoring committee within 24 hours of its notification via fax, email, or telephone. This includes all SAEs (regardless of their relationship to the study treatment).

A death occurring during the study or reported to the investigator, whether considered treatment-related or not, must be reported to the study monitoring committee.

Any SAE considered to have a causal relationship (e.g., related) with the investigational product and discovered by the investigator at any time after the study must be reported. The investigator must provide a rationale for the assessment of a causal relationship. All safety information obtained after the clinical database has been closed must be documented in the safety database, and the implications for handling the data in the clinical database must be evaluated on a case-by-case basis.

The onset date of an SAE is defined as the date on which the signs/symptoms/diagnoses became serious (i.e., meet at least one of the severity criteria). If a participant experiences an AE and it progresses to an SAE, a new SAE must be recorded. The resolution date of the original AE must be the same as the onset date of the SAE. However, when the AE is resolved and the pre-existing AE is still ongoing, this should be recorded as a new AE. The resolution date of an AE is defined as the time when symptoms disappear or when the event is considered chronic (e.g., sequelae) or stable and/or if the severity criteria are no longer applicable.

The investigator must complete the EAS report form and verify the accuracy of the information recorded on the EAS pages against the source documents. The sponsor's EAS report form must be completed in capital letters, using medical terminology, in English, and within the specified time limits. Any supporting documentation (e.g., hospital discharge summary, autopsy report/death certificate, etc.) must be submitted/transmitted with the SAE report form (attachment). The supporting information provided must not reveal the participant's identity beyond the agreed-upon study identifier. The investigator must ensure that the reported information is accurate and consistent.

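### Section 10.7.1 takes dossier-listed drug reactions out of the SAE class whatever their outcome, so a non-fatal serious listed reaction can miss both SAE status and the 24-hour report

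*Protocol*

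**What the plan says.** Protocol section 10.7.1 opens with an outcome-based definition: "A SAE is defined as any adverse medical event that, at any dose" leads to death, threat to life, hospital admission or its prolongation, lasting disability, a birth defect, or another medically significant result. It adds that a new condition, or a worsened old one, that meets these criteria counts as an SAE.

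The same section then gives a list headed "The following situations are not considered SAEs". Three of its items cover pre-planned surgery, routine health evaluations and social admissions. A further item reads "Adverse reactions associated with the investigational drugs, which are expected for such drugs according to the drug dossier registered with ANVISA". Nothing in it restricts the exclusion to reactions of minor consequence.

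Section 10.7.2 ties urgent reporting to the SAE label: "The occurrence of an SAE must be reported immediately to the study monitoring committee within 24 hours of its notification". It also has a separate sentence on deaths: "A death occurring during the study or reported to the investigator, whether considered treatment-related or not, must be reported to the study monitoring committee".

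Section 10.6.1 counts as an adverse drug reaction (ADR) only a reaction that is not yet in the ANVISA dossier, and concludes: "Thus, no reports of ADRs related to the drugs used in this study are expected". Section 10.7.3 defines a SUSAR as an ADR that is both serious and unexpected. For laboratory findings, section 10.5.4 says that an event the investigator judges serious is to be reported as an SAE, and makes no exception for listed reactions.

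**The concern.** Seriousness and expectedness answer different questions. Seriousness asks what happened to the participant. Expectedness asks whether the reaction was already known for the drug. The protocol's own scheme brings expectedness in at a later step: in 10.6.2 the reference safety information "forms the basis for assessing the predictability of an AEF for accelerated reports and annual safety reports", and in 10.7.3 it separates a SUSAR from other serious reactions. The item in 10.7.1 uses expectedness one step too early, to decide whether an event is serious at all.

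At stake is the prompt reporting of the harms that are most plausible on these two drugs. A site that follows the text would file a listed reaction leading to admission as an ordinary adverse event. It would complete no SAE form and send no 24-hour notice to the study monitoring committee. Any SAE count by arm would then leave out the type of event in which a difference between active drug and placebo is most likely.

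**Working it through.** The protocol states no figure to reproduce. The check is to take one event, a non-fatal, non-laboratory reaction listed in the dossier that leads to hospital admission, and look for any route that makes it an SAE or starts the 24-hour clock.

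1. **Definition (10.7.1).** Hospital admission is a seriousness criterion, so the event is an SAE.
2. **Exclusion list (10.7.1).** The reaction is expected under the dossier, so the event is not an SAE. Steps 1 and 2 contradict each other within one section.
3. **24-hour report (10.7.2).** The trigger is an SAE. The clause "This includes all SAEs (regardless of their relationship to the study treatment" widens the scope by causality. It does not bring back an event that the definition has already removed.
4. **ADR (10.6.1).** Only reactions absent from the dossier count, so the event is not an ADR.
5. **SUSAR (10.7.3).** This requires an unexpected ADR, so the event fails twice.
6. **Special situations (10.8.2).** Urgent reporting there again depends on an SAE having occurred, so it adds nothing.
7. **Laboratory events (10.5.4).** A serious laboratory event goes in as an SAE even if it is listed. This does not reach the example, and it is a second contradiction with the exclusion list.
8. **Deaths (10.7.2).** If the event were fatal it would be reported, but that sentence gives no deadline and does not confer SAE status.
9. **What still holds the event.** Adverse event collection under 10.2 runs from consent to the end-of-study visit. All-cause mortality and unexpected hospitalization to day 60 are secondary outcomes.

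**Direction of the effect on the SAE comparison.** Let u be the rate of unlisted SAEs, taken as equal in two arms (assumption). Let a and p be the rates of serious listed-type events on active drug and on placebo. Let f be the share of those events that investigators exclude under the item, the same in both arms because they are blinded (assumption).

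- True difference: (u + a) − (u + p) = a − p.
- Recorded difference: (u + (1 − f)a) − (u + (1 − f)p) = (1 − f)(a − p).

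If a exceeds p, which is what a known drug reaction implies, the recorded difference is smaller than the true one for any f above 0, and it is zero at f = 1. Blinding equalises f between arms but does not prevent the shrinkage.

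**Size.** The protocol gives none of a, p or f, so no estimate is possible. For scale only, if 0.5% to 2% of a 500-person arm had a serious listed reaction (assumption), that would be 0.005 × 500 = 2.5 to 0.02 × 500 = 10 events per arm open to exclusion, before setting aside any that 10.5.4 keeps in.

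**The case against.** The best case for the current text is that the events are not lost. They stay in the adverse event data. Every death must be reported. Mortality and unplanned hospitalization are checked at the scheduled visits, and outcome events are adjudicated blind under section 11.2. Section 10.7.1 itself says that new conditions meeting the criteria are SAEs, which a careful site could treat as overriding the list. All of this stands and limits the consequence. It does not restore SAE status or the 24-hour report for a non-fatal listed reaction, and it leaves each site to choose between two contradictory instructions.

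Several stronger readings are tempting, and the protocol does not support them:

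- **A reader might infer that the same event stays an SAE on placebo while it is removed on active drug.** Section 6.1 blinds the investigator, who cannot apply the item by arm. The effect is attenuation, not one-sided removal.
- **A reader might infer that the item cannot be applied under blinding at all.** An investigator could ask whether the event is listed for either drug, and the reactions named in section 7.2 overlap.
- **A reader might infer a contradiction with the rule in 10.7.2 covering SAEs regardless of relationship.** That rule concerns causality, not expectedness. The real contradictions are within 10.7.1 and with 10.5.4.
- **A reader might infer that the safety row of the table in 12.11 is biased.** That row measures adverse events, and the excluded events are still among them.
- **A reader might use the 9% dropout in section 3.3.2 as a sign of missed admissions.** Those were mild effects, found in a blinded look at the first 100 recruits that contributed to the change of metformin dose. They say nothing about serious events.
- **A reader might infer that 10.6.2 confines expectedness to accelerated reporting.** The same sentence also mentions safety monitoring of participants by regulatory agencies. That still gives no ground for using expectedness to define seriousness.

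**Conclusion.** The item is wrong as written. It contradicts the outcome-based definition in its own section and the laboratory rule in 10.5.4. Followed literally, it leaves a non-fatal, non-laboratory, dossier-listed serious reaction outside the SAE, ADR and SUSAR classes and outside the 24-hour report. For a fatal listed reaction a reporting duty remains, but without a time limit.

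The consequence is a gap in expedited safety reporting and, in direction, a smaller between-arm difference in any SAE count. The direction assumes that serious listed reactions are more frequent on active drug than on placebo and that blinded investigators exclude them at a similar rate in each arm. The size is unknown. The point does not mean that these harms vanish from the trial. Because it concerns prompt recognition of serious harm and the text gives a wrong result, it should be corrected whatever the number of events affected.

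**What to change.** Amend the protocol as follows:

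- Delete the item on expected reactions from the list in 10.7.1.
- State that every event meeting a 10.7.1 seriousness criterion is recorded as an SAE and reported within 24 hours, whether or not it is listed for either drug. This would cover fatal events too.
- Use the registered dossier only to decide whether a serious, related event is unexpected, that is, for the SUSAR decision in 10.7.3.
- Revise 10.6.1 so that a listed reaction is still an ADR. Deleting the 10.7.1 item alone would leave this parallel exclusion, on which the SUSAR definition is built.
- Check that 10.5.4, 10.6.1, 10.7.1 and 10.7.2 then agree.
- Ask sites to re-check adverse events already recorded, and to upgrade and report any that met a seriousness criterion but were left out under this item.

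The cost is one amendment, some extra SAE forms and a site-level look back through recorded events. Sample size, randomization and the efficacy analysis do not change.

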10.7.2 Reporting of serious adverse events

The SAE reporting period begins when the consent form is signed by the participant. The SAE reporting period ends at the 90-day visit.

The occurrence of an SAE must be reported immediately to the study monitoring committee within 24 hours of its notification via fax, email, or telephone. This includes all SAEs (regardless of their relationship to the study treatment).

A death occurring during the study or reported to the investigator, whether considered treatment-related or not, must be reported to the study monitoring committee.

Any SAE considered to have a causal relationship (e.g., related) with the investigational product and discovered by the investigator at any time after the study must be reported. The investigator must provide a rationale for the assessment of a causal relationship. All safety information obtained after the clinical database has been closed must be documented in the safety database, and the implications for handling the data in the clinical database must be evaluated on a case-by-case basis.

The onset date of an SAE is defined as the date on which the signs/symptoms/diagnoses became serious (i.e., meet at least one of the severity criteria). If a participant experiences an AE and it progresses to an SAE, a new SAE must be recorded. The resolution date of the original AE must be the same as the onset date of the SAE. However, when the AE is resolved and the pre-existing AE is still ongoing, this should be recorded as a new AE. The resolution date of an AE is defined as the time when symptoms disappear or when the event is considered chronic (e.g., sequelae) or stable and/or if the severity criteria are no longer applicable.

The investigator must complete the EAS report form and verify the accuracy of the information recorded on the EAS pages against the source documents. The sponsor's EAS report form must be completed in capital letters, using medical terminology, in English, and within the specified time limits. Any supporting documentation (e.g., hospital discharge summary, autopsy report/death certificate, etc.) must be submitted/transmitted with the SAE report form (attachment). The supporting information provided must not reveal the participant's identity beyond the agreed-upon study identifier. The investigator must ensure that the reported information is accurate and consistent.

At a minimum, the following information must be provided at the time of creating the initial SAE report:

- Study name and/or number
- The participant's number, age, and sex/gender
- The description/exact wording of the event (including the onset date of the SAE, its outcome, and the reason it was considered serious)
- Relationship to the investigational medical product (e.g., causality)

- Dose of the investigational medical product (number of packages) and dates of administration
- Action taken regarding the investigational medical product
- Severity of the event
- Name and address of the investigator
- Name of the reporter (including center name or number and country) and,
- Dated signature of the investigator or sub/co-investigator

When using electronic methods for reporting SAEs, some of the information listed above may be generated by the electronic system. Since SAEs are also AEs, the information in the AE clinical record and the SAE form must be consistent.

Follow-up information must be handled in the same manner and reported within the same timeframe as the initial SAE report. A safety contact sheet will be provided to the Investigator (before the first participant provides informed consent), detailing all applicable contact information for safety reporting. This contact sheet will be kept up to date, and any changes will be provided immediately to the Investigator.

Whenever possible, the investigator should report a diagnosis rather than individual signs and symptoms or abnormal laboratory values.

In the event of a fatal outcome, the investigator should provide a working diagnosis (the event that caused the outcome, e.g., death due to fatal myocardial infarction) rather than reporting only the death; and an autopsy report should be provided when possible. If the cause of death becomes known later (e.g., after autopsy), this working diagnosis should be replaced by the established cause of death.

All reported SAEs, regardless of their relationship to the investigational product, must be followed up until resolution or stabilization, or until the participant is lost to follow-up and can no longer be contacted. At the EoS visit, updates must be recorded and submitted. In circumstances where the investigator cannot contact the participant (or their relatives), the investigator must provide a written statement (recorded in the participant's source documents) to the study steering committee, confirming that the participant is no longer being followed up.

10.7.3 SUSARs

A suspected unexpected serious adverse reaction (SUSAR) is defined as any serious and unexpected adverse drug reaction (ADR).

For the purposes of this protocol, the occurrence of SUSARs is not expected, since the drugs were approved several years ago by ANVISA and have been used in hundreds of thousands of participants, and potential adverse reactions and/or idiosyncrasies are already well known to regulatory authorities.

The sponsor or investigator must notify the ethics committee and regulatory authorities of all SUSARs and other types of AEs (if applicable) in accordance with local safety requirements.

10.8 Special Situations

10.8.1 Definition of special situations

The following situations are defined as special:

Medication abuse: persistent or sporadic, intentional, and excessive use of the study medication by the participant (not for therapeutic purposes)

Medication error: An unintentional error in the prescribing, dispensing, or administration of an investigational medicinal product (IMP) during the study. (A medication error is any preventable event that may cause or lead to the inappropriate use of the medication or harm to the patient while the medication is under the control of the healthcare professional or the patient).

Medication misuse: Intentional and inappropriate use of an EFP by the participant for therapeutic purposes that does not conform to the dose, route of administration, and/or indication(s) specified in the protocol (e.g., the participant deliberately took the medication twice daily instead of once daily)

Drug overdose: administration of an amount of the study drug equivalent to three times the maximum dose permitted by the protocol per administration or per day.

Drug-drug interaction involving the study drug

Unexpected therapeutic or clinical benefit from the use of the study medication

Suspected AEs associated with medication errors or unauthorized use (e.g., overdose) must be reported and documented in the medical record.

10.8.2 Recording and reporting of special situations

All special situations must be documented in the participant's source documents. If a special situation leads to a serious adverse event (SAE), the event must be reported immediately within 24 hours of notification via fax, email, or telephone.

10.8.3 Exposure during pregnancy and birth events

10.8.3.1 Definition of exposure during pregnancy and birth events

Decades of experience with metformin use suggest that this medication should not be prescribed to pregnant participants without a careful assessment of the risks and benefits of its use during this phase. Thus, pregnancy is not expected during the treatment phase, and women must use contraceptive methods to prevent pregnancy (if necessary, we will provide an effective contraceptive method for use during the medication period).

When a female participant becomes pregnant during the study and has received study treatment, the pregnancy outcome must be monitored, and the safety of the mother and fetus must be assessed. Therefore, the outcome of all such pregnancies (including normal births) must be monitored and documented, even if the participant has been withdrawn from the study or the study has been terminated.

A female participant must immediately inform the investigator if she becomes pregnant during the study. The investigator must counsel the participant and discuss the risks and benefits of continuing the study medication and advise the patient on follow-up until the child is born.

The investigator is responsible for monitoring the participant and the pregnancy outcome and for reporting this information to the sponsor. Every effort should be made to collect information on the pregnancy outcome up to 90 days after delivery (or otherwise, as appropriate).

